#### **P-gp substrates**

Aliskiren, ambrisentan, colchicine, dabigatran etexilate, digoxin, everolimus, fexofenadine, lapatinib, loperamide, maraviroc, nilotinib, ranolazine, saxagliptin, sirolimus, sitagliptin, talinolol, tolvaptan, topotecan

#### **BCRP** substrates

Methotrexate, mitoxantrone, irinotecan, lapatinib, rosuvastatin, sulfasalazine, topotecan

# OATP1B1/1B3 substrates

Atrasentan, atorvastatin, ezetimibe, fluvastatin, glyburide, rosuvastatin, simvastatin acid, pitavastatin, pravastatin, repaglinide, telmisartan, valsartan, olmesartan

# **BCRP** inhibitors

Geftinib

# Appendix IV - Cairo Bishop Guidelines

#### Cairo-Bishop definition of laboratory tumor lysis syndrome:

Either the presence of two or more of the following laboratory changes within 3 days before or seven days after cytotoxic therapy **OR** a 25% change above or below normal.

Element	Value	Change from baseline			
Uric Acid	≥476 μmol/L (8mg/dL)	or 25% increase			
Potassium	$\geq 6.0 \text{ mmol/L} (\text{or } 6\text{mEq/L})$	or 25% increase			
Phosphorus	$\geq$ 1.45 mmol/L (4.5 mg/dL) for adults	or 25% increase			
Calcium	≤1.75 mmol/L (7mg/dL)	or 25% decrease			

Adapted from the Guidelines for the management of pediatric and adult tumor lysis syndrome: an evidence-based review

# Appendix V – Quality of Life and Fatigue Questionnaires

# ٩

#### EORTC QLQ-C30 (version 3)

We are interested in some things about you and your health. Please answer all of the questions yourself by circling the number that best applies to you. There are no "right" or "wrong" answers. The information that you provide will remain strictly confidential.

		Not at All	A Little	Quite a Bit	Very Much
	Do you have any trouble doing strenuous activities, like carrying a heavy shopping bag or a suitcase?	1	2	3	4
	Do you have any trouble taking a long walk?	1	2	3	4
	Do you have any trouble taking a short walk outside of the house?	1	2	3	4
	Do you need to stay in bed or a chair during the day?	1	2	3	4
	Do you need help with eating, dressing, washing yourself or using the toilet?	1	2	3	4
Du	ring the past week:	Not at	A Little	Quite a Bit	Very Much
	Were you limited in doing either your work or other daily activities?	1	2	3	4
	Were you limited in pursuing your hobbies or other leisure time activities?	(I)	2	3	4
	Were you short of breath?	1	2	3	4
	Have you had pain?	1	2	3	4
0.	Did you need to rest?	1	2	3	4
1.	Have you had trouble sleeping?	1	2	3	4
2.	Have you felt weak?	1	2	3	4
3.	Have you lacked appetite?	1	2	3	4
4.	Have you felt nauseated?	1	2	3	4
5.	Have you vomited?	1	2	3	4

During the	e past week:	Not at All	A Little	Quite a Bit	Very Much
16. Have y	ou been constipated?	1	2	3	4
17. Have y	ou had diarrhea?	1	2	3	4
18. Were y	ou fired?	1	2	3	4
19. Did pa	in interfere with your daily activities?	1	2	3	4
	ou had difficulty in concentrating on things, ding a newspaper or watching television?	1	2	3	4
21. Did yo	a feel tense?	1	2	3	4
22. Did yo	a worry?	1	2	3	4
23. Did yo	a feel irritable?	1	2	3	4
24. Did yo	a feel depressed?	1	2	3	4
25. Have y	ou had difficulty remembering things?	1	2	3	4
	ur physical condition or medical treatment ed with your family life?	1	2	3	4
	ur physical condition or medical treatment ed with your social activities?	À 1	2	3	4
	ur physical condition or medical treatment you financial difficulties?		2	3	4

For the following questions please circle the number between 1 and 7 that best applies to you

 29. How would you rate your overall health during the past week?

 1
 2
 3
 4
 5
 6
 7

 Very poor
 Excellent

30. How would you rate your overall quality of life during the past week?

l 2 3 4 5 6 7 Very poor Excellent

© Copyright 1995 EORTC Study Group on Quality of Life. All rights reserved. Version 3.0

# Functional Assessment of Chronic Illness Therapy (FACIT) Fatigue Scale (Version 4)

Below is a list of statements that other people with your illness have said are important. Please circle or mark one number per line to indicate your response as it applies to the past 7 days.

		Not At All	A Little Bit	Somewhat	Quite a Bit	Very Much
1	I feel fatigued	0	1	2	3	4
2	I feel weak all over	0	1	2	3	4
3	I feel listless ("washed out")	0	1	2	3	4
4	I feel tired	0	1	2	3	4
5	I have trouble starting things					
	because I am tired	0	1	2	3	4
6	I have trouble finishing things					
	because I am tired	0	1	2	3	4
7	I have energy	0	1	2	3	4
8	I am able to do my usual activities	0	1	2	3	4
9	I need to sleep during the day	0	1	2	3	4
10	I am too tired to eat	0	1	2	3	4
11	I need help doing my usual activities	0	1	2	3	4
12	I am frustrated by being too tired					
	to do the things I want to do	0	1	2	3	4
13	I have to limit my social activity					
	because I am tired	0	1	2	3	4

Scoring: Items are scored as follows: 4=Not At All; 3=A Little Bit; 2=Somewhat; 1=Quite A Bit; 0=Very Much, EXCEPT items #7 and #8 which are reversed scored. Score range 0-52. A score of less than 30 indicates severe fatigue. The higher the score, the better the quality of life.

http://www.facit.org/FACITOrg/Questionnaires

#### Two minute walk test instructions

Patients will need to walk for a total of two minutes and the unit of length will be measured in "feet." Assistive devices can be used but should be kept consistent and documented from test to test. If physical assistance is required, this test should not be performed. Walking path (i.e. laps up and down hallway) should be predetermined and feasible to measure.

\* Adapted from NIH toolbox

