# 2.2.2 Secondary Endpoints

- Overall response rate (CR/CRi), as defined by the revised IWG criteria. See Section 9.1.
- Anti-leukemic activity (CR/CRi/PR), as defined by the revised IWG criteria. See Section 9.1.
- Adverse effects will be characterized using the CTCAE v5 criteria.
- Relapse-free survival (RFS), event-free survival (EFS, and overall survival (OS). See Section 9.2
- The European Organization for the Research and Treatment of Cancer 30 item questionnaire (EORTC QLQ-C30), The Functional Assessment of Cancer Therapy Fatigue (FACT-Fatigue) questionnaire, two-minute walk test, and timed chair stands will be performed at trial entry and every other month for 1 year.

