# 3.1 Inclusion Criteria

Subjects must meet all of the following applicable inclusion criteria to participate in this study:

- 1. Written informed consent and HIPAA authorization for release of personal health information. **NOTE:** HIPAA authorization may be included in the informed consent or obtained separately.
- 2. Ages 18 to 75 years at the time of consent.
- 3. ECOG Performance Status of 0-2 within 7 days prior to registration; see Appendix I.
- 4. Patients must have AML, as defined, that is relapsed or refractory. Prior therapy including chemotherapy, immunotherapy, biological or targeted therapy (e.g. FMS-like tyrosine kinase-3 (FLT3) inhibitors, other kinase inhibitors, azacitidine, ATRA) is allowed.
- 5. CD33 expression (by flow or IHC) in at least 20% of the leukemia blasts per local pathologist.
- 6. Prior cancer treatment must be completed at least 21 days prior to registration and the subject must have recovered from all reversible acute toxic effects of the regimen (other than alopecia) to  $\leq$ Grade 1 or baseline.
- 7. Demonstrate adequate organ function as defined in the table below; all screening labs to be obtained within 28 days prior to registration.

System	Laboratory Value	
Renal		
Calculated creatinine clearance	$\geq$ 30 cc/min using the	
Calculated creatinine clearance	Cockcroft-Gault formula	
Hepatic		
Bilirubin	$\leq 1.5 \times$ upper limit of normal (ULN)	
Aspartate aminotransferase (AST)	≤2 × ULN	
Alanine aminotransferase (ALT)	≤2 ×ULN	

- 8. Females of childbearing potential must have a negative serum or urine pregnancy test within 7 days prior to registration. **NOTE:** Females are considered of child bearing potential unless they are surgically sterile (have undergone a hysterectomy, bilateral tubal ligation, or bilateral oophorectomy) or they are naturally postmenopausal for at least 12 consecutive months
- 9. Females of childbearing potential and males must be willing to use effective contraception during treatment and for at least 30 days after the last dose of Venetoclax. Females will be advised to use effective contraception for at least 6 months after the last dose of Gemtuzumab and males for at least 3 months after the last dose of Gemtuzumab.

10. As determined by the enrolling physician or protocol designee, ability of the subject to understand and comply with study procedures for the entire length of the study

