10: Whole blood to be collected pre-treatment, Cycle 1 Day +3 ( $\pm 1$  day), end of induction, end of consolidation, pre-treatment cycle 7 day 1 (i.e.  $\sim 6$  mo), pre-treatment cycle 13 day 1 (i.e.  $\sim 12$  mo), and relapse. See section 8. See Correlative Laboratory Manual (CLM) for collection, labeling, processing, and shipping instructions.

11: Bone marrow aspirate to be collected pre-treatment, end of induction, end of consolidation, pre-treatment cycle 7 day 1 (i.e.  $\sim$ 6 mo), pre-treatment cycle 13 day 1 (i.e.  $\sim$ 12 mo), and relapse. See CLM for collection, labeling, processing, and shipping instructions. Left-over samples will be banked for potential future studies, with patient consent. See section 8.

12: Pre-treatment evaluation includes buccal swab, whole blood collection, QOL (QLQ-C30, FACT-Fatigue), walk test, and chair stands. Pre-treatment bone marrow aspirate will be collected at screening. Aspirate collection for correlative studies is required prior to therapy.

13: QOL (QLQ-C30, FACT-Fatigue), walk test and chair stands to be performed pre-treatment, at the end of consolidation, every other cycle starting with Cycle 4 and throughout long term follow up.

14: Whole Blood, Serum and Plasma for banking to be collected pre-treatment, end of induction, end of consolidation, pre-treatment cycle 7 day 1 (i.e. ~6 mo), pre-treatment cycle 13 day 1 (i.e. ~12 mo), and relapse. See CLM for collection, labeling, processing, and shipping instructions. 15: It is suggested that patients should not receive HSCT conditioning within 2-3 months of last Gemtuzumab dose and that total body irradiation (TBI)/ total marrow irradiation (TMI) as part of a HSCT conditioning regimen be avoided, if possible, per discretion of the site PI.

09JUN2022

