# **12.6.3 Other Planned Analyses**

Descriptive characteristics of patients will be reported in tabular form along with the dates of trial opening and closing, indicating the total number of patients enrolled and accounting for all patients considered for entry (flow diagram). Patients found to be ineligible will be indicated along with their reasons for ineligibility and whether they received any study therapy. Of the included subjects, the number of patients who were evaluable for toxicity and response (secondary objectives, see section **12.2.2**) will be reported.

Drug administration by dose level will be reported in tables detailing the total number of patients treated, number of doses or cycles received at dose level, and the number of incomplete cycles, including brief descriptions of what happened in dose escalation if intermediate dose levels or deviations from study protocol resulted. Any dose holds, reductions, and delays, and permanent discontinuation of study treatments will be summarized with reasons for each. Finally, summaries of dose intensity will be estimated, including how many patients were able to receive each planned dose intensity of Venetoclax administered with Gemtuzumab Ozogamicin.

Tables of adverse effects displaying the worst grade by dose level will be reported, including columns or each grade and "any grade" adverse effects. Separate tables report hematological and non-hematological effects will be reported according to dose escalation.

Descriptive tables reporting frequencies and means or medians of scores of the EORTC QLQ-C30 and FACT-Fatigue questionnaire, two-minute walk test, and timed chair stand will be created for D0 (trial entry) and subsequent months of follow up. Generalized linear modeling of continuous scores or ordinal values accounting for correlation and repeated will be performed to determine differences between groups

and characteristics considered to be potential confounding factors. Given a threshold value indicating a substantial degree of the outcome (i.e., quality of life, fatigue and physical function), generalized estimating equation models with a binomial distribution and unstructured correlation covariance will be used to produce odds ratios (OR) and robust 95% CI for the relation of dose and clinical characteristics to each outcome.

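### The two-minute walk test is not done when a patient needs physical assistance, and no score or analysis rule covers those visits, so the walk results can overstate preserved function

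*Combined protocol and SAP*

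**What the plan says.** Section 2.2.2 makes the test a secondary endpoint: "two-minute walk test, and timed chair stands will be performed at trial entry and every other month for 1 year". The study calendar (Section 7, footnote 13) gives a somewhat different schedule: before treatment, at the end of consolidation, then "every other cycle starting with Cycle 4 and throughout long term follow up".

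Appendix V measures distance in feet and sets two conditions. Devices are permitted: "Assistive devices can be used but should be kept consistent and documented from test to test". Hands-on help is not: "If physical assistance is required, this test should not be performed". No distance, category or reason code is assigned when the test is withheld.

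Section 12.6.2 plans generalized linear modelling of quality of life, fatigue and physical function. Section 12.6.3 plans three things:

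- "Descriptive tables reporting frequencies and means or medians of scores of the EORTC QLQ-C30 and FACT-Fatigue questionnaire, two-minute walk test, and timed chair stand", at trial entry and in later months.
- "Generalized linear modeling of continuous scores or ordinal values accounting for correlation and repeated will be performed", to look at differences between groups.
- A dichotomised analysis using "generalized estimating equation models with a binomial distribution and unstructured correlation covariance", relating dose and clinical characteristics to each outcome. No threshold value is given.

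Section 12.6 does not say how a walk test that was not performed enters any of these, states no missing-data assumption for them, and plans no sensitivity analysis.

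**The concern.** The value is absent because of what it would have shown. A patient who can no longer walk without someone's help has had about as poor a result as the endpoint can register, and that visit contributes nothing. Entry requires "ECOG Performance Status of 0-2 within 7 days prior to registration", so a need for hands-on help would mostly arise after baseline, which is the change the endpoint is there to detect.

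The planned methods do not protect against this. An unweighted GEE needs data missing completely at random, and a likelihood-based repeated-measures model needs data missing at random; this mechanism may violate both. The threshold model shows the problem most plainly, since a patient who cannot walk without help belongs on the poor side of any sensible cut-off, yet is dropped from that visit.

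At stake is one of two objective measures behind the secondary objective on physical function. Section 1.3 hopes to maintain or improve quality of life, and the possible error runs in the direction of that hope.

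**Working it through.** **Inputs.** The documents give the rule (Appendix V), the endpoint (2.2.2) and the analyses (12.6.2, 12.6.3). They give no expected proportion needing assistance, no mean or SD for walk distance and no target difference, so there is no figure of the plan to reproduce. Every number below except cohort size is an assumption used to show direction and range.

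**Step 1: direction.** Let a share q go untested, and let ρ be the correlation between poor walking distance and needing assistance. For a normal distance, the mean among those tested exceeds the mean among all by

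ρ × φ(z_q) / (1 − q), in SD units.

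For q = 0.20 and ρ = 1 this is 0.280 / 0.80 = 0.35 SD.

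| Share untested | ρ = 0 | ρ = 0.5 | ρ = 1 |
|---|---|---|---|
| 5% | 0 | 0.05 | 0.11 |
| 10% | 0 | 0.10 | 0.20 |
| 20% | 0 | 0.18 | 0.35 |
| 30% | 0 | 0.25 | 0.50 |

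The shift is upward whenever need for help tracks poor walking, and zero only if the two are unrelated.

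**Step 2: simulated illustration.** 400,000 patients; baseline 450 ft (SD 100); change with SD 90; untested if the follow-up distance would fall below 200, 250 or 300 ft. *By-visit* is the mean of those tested at follow-up minus the mean of everyone at baseline. *Paired* is the mean change among those tested at both visits. The last two columns score untested visits as 0 ft. All values are in feet.

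| True mean change | Untested | By-visit | Paired | Mean with 0 ft | Median with 0 ft |
|---|---|---|---|---|---|
| -30 | 5% | -15 | -23 | -37 | -30 |
| -30 | 10% | -3 | -18 | -49 | -32 |
| -30 | 19% | +14 | -10 | -72 | -35 |
| -60 | 8% | -38 | -50 | -71 | -61 |
| -60 | 15% | -23 | -44 | -87 | -63 |
| -60 | 25% | -3 | -34 | -115 | -70 |
| -100 | 13% | -67 | -85 | -117 | -103 |
| -100 | 35% | -22 | -65 | -174 | -124 |

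By-visit means range from a modest understatement to a flat or slightly improved picture. Paired analyses understate the decline in every row but still show one.

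**Step 3: choice of score.** Entering 0 ft in a mean overshoots: -87 ft against a true -60 ft at 15% untested. The median change stays close (-63 ft) and drifts to -70 ft at 25%. A lowest-rank score with medians or ranks is therefore the better repair, and 0 ft in a mean is not.

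**Step 4: threshold model and small cohorts.** Suppose one patient of six needs help and the other five are above threshold. The plan as written counts 0 of 5 below threshold; counting the untested patient gives 1/6 = 17%. Dose cohorts have 3 to 6 patients, so one omitted patient can change what a table shows.

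**The case against.** Much can be said on the other side.

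- The trigger is narrow. Patients with a cane or walker are still tested, so it is wrong to describe the tested group as those who walk unaided. The documents give no reason to expect a particular share needing hands-on help.
- The decline would partly show elsewhere: ECOG status at scheduled visits, the QLQ-C30 items on a short walk and on self-care, and the fatigue scale's item on needing help. The planned frequencies might also reveal a fall in the number tested, though not why.
- Death, removal from study (Section 5.4) and telephone follow-up (Section 7.2) also remove walk data and may matter more.
- This is one descriptive secondary measure in a dose-finding trial of 15 to 24 patients (Synopsis; Section 12.3 says 18 to 24) whose primary endpoint is dose-limiting toxicity.
- The eCRF is not among the documents, so a reason-not-done field may already exist.

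All of this stands and keeps the point small. It does not remove it: the walk distance will still be tabulated and modelled in its own right, and this is the one source of missing values where the patient is present and the functional state is known.

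Three stronger readings are tempting and should not be drawn. A reader might infer that the plan will show function preserved when it is not; the illustration gives that only in some by-visit scenarios and in no paired one. A reader might infer that the chair-stand test records the same patient as 0 while the walk test records nothing; Appendix V assigns no 0 there, and its practice stands and readiness condition could leave that test undone too. A reader might infer that the dose relation is biased toward no harm; that requires more patients to need help at higher doses, for which the documents give no figure, and cohorts of 3 to 6 could not estimate such a relation reliably anyway.

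**Conclusion.** The point holds in a limited form. The plan withholds the walk test from patients who need hands-on help and gives those visits no score and no analysis rule, so the summaries and models in 12.6.2 and 12.6.3 can overstate preserved walking function. The direction rests on one assumption, that needing help goes with poor walking. The size is unknown; the figures above rest on assumed means, SDs and cut-offs and on untested patients being exactly those with the shortest distances, which makes the illustrated bias close to the largest for a given share. Any effect on the dose comparison is conditional. Nothing here touches the primary endpoint or the dose decision, and the importance is minor.

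**What to change.** Keep the instruction not to perform the test. Then:

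1. Record *not performed, needs physical assistance* on the eCRF, separately from every other reason.
2. Report the number and proportion unable at each visit, by dose level.
3. In the walk-distance analysis give these visits the lowest rank, and make medians or rank-based summaries the main presentation, not means with 0 ft.
4. Count these visits as below threshold in the binomial GEE.
5. Show the tested-patients-only result as a sensitivity analysis.
6. Leave tests missed for unrelated reasons, such as telephone follow-up, as missing.

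The cost is one data field (if not already present) and a few lines in Section 12.6.3, with no new procedure for the patient. The reason should be captured at the visit, because it may not be recoverable later. The downside is that means stop being the natural summary of walk distance. The change does not deal with walk data lost through death or removal from study, which needs its own statement.

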#### **30** second chair stand test

Patients should start in the sitting position with back straight, arms crossed over chest and feet flat on the floor. The chair should be placed against a wall for stability. Observe 1-2 practice stands to ensure proper form and adequate balance. Once the patient is ready, measure the number of times he/she can rise to a full stand and then return to a fully seated position in 30 seconds. If the patient is more than half way up at the end of the 30 seconds, count this as a full stand.
